1. INTRODUCTION

The purpose of this statistical analysis plan (SAP) is to describe the planned analyses to be included in the Clinical Study Report(s) (CSR) for Protocol 218128.

This SAP covers the analyses planned for the following Statistical Analysis Complete (SAC) deliverables:

- Part A Interim Analysis (IA)
- Part A Day 29
- Part A Week 24
- Part A Week 35
- Part C Cohort 1 IA
- Part C Cohort 1 Day 29
- Part C Cohort 1 Week 24
- Part C Cohort 1 Week 35

At the time of writing this SAP, an optional Part B or optional Part C Cohort 2 has not been confirmed. Under the condition that Part B or Part C Cohort 2 is required, a SAP amendment will be created to include Part B or Part C Cohort 2. Details of the planned analyses are provided in Section [4.7](#).

Note that in line with the guidelines, this SAP will use the term “participant”, while all data displays (Tables, Figures & Listings [TFL]) produced as part of the planned dry-run and the SAC, will use the term “subject” which reflects GlaxoSmithKline (GSK) Data Display Standards terminology.

1.1. Objectives, Estimands and Endpoints

Objectives	Endpoints
Primary	
Pharmacokinetics Part A: To estimate the relative bioavailability of 100 mg/mL IM sotrovimab at the dorsogluteal injection site relative to the 62.5 mg/mL formulation administered dorsogluteally through Day 29	Sotrovimab pharmacokinetics (PK) parameters: AUC_{D1-29} and C_{max}
Safety Part A: To evaluate the safety and tolerability profile of 100 mg/mL IM sotrovimab and	Incidence of all adverse events (AEs), serious adverse events (SAEs), and adverse events of special interest (AESI) through Day 29

Objectives	Endpoints

the 62.5 mg/mL formulation at the dorsogluteal injection site through Day 29
 
Part C:
 
To evaluate the safety and tolerability profile of IV sotrovimab in Cohort 1 through Day 29
	
Secondary	

Pharmacokinetics
 
Part A:
 
To estimate the relative bioavailability of 100 mg/mL IM sotrovimab at 2 alternative injection sites (anterolateral thigh, and deltoid) relative to the 62.5 mg/mL formulation administered dorsogluteally through Day 29
 
Part C:
 
To characterize the PK of IV sotrovimab in Cohort 1 through Day 29
	Sotrovimab PK parameters: AUC_{D1-29} and C_{max}

Pharmacokinetics
 
Part A:
 
To estimate the relative bioavailability of 100 mg/mL IM sotrovimab at 3 injection sites (dorsogluteal, anterolateral thigh, and deltoid) relative to the 62.5 mg/mL formulation administered dorsogluteally through Week 24
	Sotrovimab PK parameter: AUC_{inf}

Pharmacokinetics
 
Part A:
 
To characterize the PK of 100 mg/mL and 62.5 mg/mL IM sotrovimab through Day 29 and Week 24
	Serum PK of sotrovimab

Objectives	Endpoints

Part C:
 
To characterize the PK of IV sotrovimab in Cohort 1 through Day 29 and Week 24
	

Safety
 
Part A:
 
 • To evaluate the safety and tolerability profile of 100 mg/mL IM sotrovimab administered at anterolateral thigh and deltoid injection sites and the 62.5 mg/mL formulation administered dorsogluteally through Day 29 • To evaluate the safety and tolerability profile of 100 mg/mL IM sotrovimab administered at the dorsogluteal, anterolateral thigh, and deltoid injection sites and the 62.5 mg/mL formulation administered dorsogluteally through Week 35 
Part C:
 
To evaluate the safety and tolerability profile of IV sotrovimab in Cohort 1 through Week 35
	
Part A: Incidence of AEs, SAEs, and AESI through Day 29/Week 35
 
Part C: Incidence of AEs, SAEs, and AESI through Week 35

Other Safety	

Part A:
 
To evaluate the safety and tolerability of sotrovimab following IM administration through Day 29 and Week 35
 
Part C:
 
To evaluate the safety and tolerability of IV sotrovimab in Cohort 1 through Day 29 and Week 35
	Incidence of clinically significant changes in vital signs and laboratory abnormalities change from baseline through Day 29 and Week 35
Exploratory	

PRO (Part A)
 
Evaluate the pain, ISR, and acceptability of both the 62.5 mg/mL and 100 mg/mL
	
 • Totally acceptable or very acceptable pain and totally acceptable or very acceptable local reaction

Objectives	Endpoints
formulations of sotrovimab administered intramuscularly	
acceptability score on PIN_TS3.0 at Days 1, 2, 3, 5, and 8.
 
• Pain intensity on pain-NRS at 15 minutes, 30 minutes and 1 hour after dosing and before bedtime on Day 1, and Days 2, 3, 5, and 8• Scores of PIN_TS3.0 domains (bothersomeness of ISRs, impact on sleep, impact on movement), and scores of four individual items (anxiety before injection, bothersomeness during injection, satisfaction with the injection system, and willingness to receive as a treatment) on Days 1, 2, 3, 5, and 8

CCI

Co-primary Estimands (Part A)

The primary clinical question of interest is: what is the relative bioavailability and safety profile of 100 mg/mL IM sotrovimab administered at the dorsogluteal injection site relative to the 62.5 mg/mL IM formulation administered dorsogluteally in participants through Day 29?

The PK primary estimand is described by the following attributes:

- Population: Male or female healthy participants aged 18 to 65 years who would be able to complete the IM dose.
- Endpoints: Sotrovimab serum PK parameters: AUC_{D1-29} and C_{max} .
- Treatments: 100 mg/mL IM sotrovimab vs 62.5 mg/mL IM sotrovimab (dorsogluteal injections).
- Strategy for intercurrent event: The intercurrent event of interest is participants receiving an incomplete IM dose. The strategy for handling this intercurrent event will be a Principal Stratum Strategy, where we are only interested in the strata of participants who would be able to receive a complete IM dose. Exclusion of participants who did not receive a complete IM dose will not introduce bias as the reasons for dose interruption are not related to their PK.
- Population-level summary: The point estimate for the ratio of the geometric means of 100 mg/mL treatment group compared to the 62.5 mg/mL treatment group and the related 90% confidence interval (CI) will be calculated.

The Safety primary estimand is described by the following attributes:

- Population: Male or female healthy participants aged 18 to 65 years.
- Endpoints: Incidence of all AEs, SAEs, and AESI through Day 29 (i.e., all events on the database at the time of data cut-off [DCO]).
- Treatments: 100 mg/mL IM sotrovimab and 62.5 mg/mL IM sotrovimab (dorsogluteal injections).
- Strategy for intercurrent event: The intercurrent event of interest is participants receiving an incomplete IM dose. The strategy for handling this intercurrent event will be a Treatment Policy Strategy, where all safety data after the intercurrent event will be included.
- Population-level summary: Frequency and percentage of participants.

Primary Estimand (Part C)

The primary clinical question of interest is: what is the safety and tolerability of IV infusion of sotrovimab at 3000 mg dose in Cohort 1?

The Safety primary estimand is described by the following attributes:

- Population: Male or female healthy participants aged 18 to 65 years.
- Endpoints: Incidence of all AEs, SAEs, and AESI through Day 29 (i.e., all events on the database at the time of DCO).

[figure not shown]
- Treatments: Single IV infusion of sotrovimab at 3000 mg dose in Cohort 1.
- Strategy for intercurrent event: The intercurrent event of interest is participants receiving an incomplete IV dose. The strategy for handling this intercurrent event will be a Treatment Policy Strategy, where all safety data after the intercurrent event will be included.
- Population-level summary: Frequency and percentage of participants.

Rationale for Estimands:

Two different strategies are proposed for the same intercurrent event of participants receiving an incomplete IM/IV dose, as interest lies in:

- the PK of treatment effect in participants who received complete dose, and
- safety of treatment effect for any level of exposure to study intervention.

1.2. Study Design

Overview of Study Design and Key Features	
	
Part A:
 
On Day 1, participants will be randomized in a 2:2:1:1 ratio to the following four treatment arms:
 
○ 500 mg IM of 62.5 mg/mL sotrovimab administered into the dorsogluteal muscles○ 500 mg IM of 100 mg/mL sotrovimab administered into the dorsogluteal muscles○ 500 mg IM of 100 mg/mL sotrovimab administered into the anterolateral thigh muscles○ 500 mg IM of 100 mg/mL sotrovimab administered into the deltoid muscles 
● Approximately 190 participants will be enrolled to achieve approximately 150 evaluable participants across the four treatment arms.● Visit Frequency: all participants will receive a single dose of sotrovimab on Day 1. Participants will need to return to the study site on Days 2, 3 and 5 and at Weeks 2, 3, and 4 (Day 29). At Weeks 8, 12, 20, and 24, the participants will need to return to the site or have a home visit. At Week 35, the participants will have a phone call visit. Additionally, participants will need to complete a patient-reported outcome (PRO) assessment at home on Day 1. Participants will also need to complete a PRO assessment at the site on Days 2, 3, 5, and 8. Screening assessment will be performed within 28 days prior to dosing, leading to a maximum study duration of 39 weeks.● Follow-up will occur via site and home visits, and a phone call visit at Week 35. 
Part C Cohort 1:
 
● Enough healthy participants will be screened to ensure approximately 200 participants (intend to target up to approximately 20 Japanese participants) are enrolled in Cohort 1.● Cohort 1: Single IV infusion of sotrovimab at 3000 mg dose, infused over 60 minutes (100 mg/mL, diluted as per pharmacy manual).● Initial dosing in Cohort 1 will be staggered so that the first 2 participants will be considered sentinels and will be dosed 3000 mg sotrovimab administered intravenously at the same clinical trial site. After at least 24 hours (post dose), and provided the investigator considers the safety and tolerability of the sentinels to be acceptable, the remainder of the participants will be dosed as non-sentinel`.● Approximately 170 additional participants will then be enrolled into this cohort● Visit frequency: all participants in Part C will receive a single dose of sotrovimab on Day 1 at the study site; will return to the study site on Days 2, 3, and 5 and at Weeks 2, 3, and 4 (Day 29); will also return to the study

Overview of Study Design and Key Features	
	site or have a home visit at Weeks 8, 12, 20 and 24. At Week 35, the participants will have a phone call visit. Participants can be screened up to 28 days before dosing; therefore, the maximum duration a participant will be in the study is 39 weeks.
Study Intervention	
 Part A: Sotrovimab IM Injection, 62.5 mg/mL or 100 mg/mL will be provided in 1 or 2 single-use vials. Part C Cohort 1: IV Infusion of sotrovimab 100 mg/mL (diluted as per pharmacy manual) will be provided in 12 single-use vials. In Part A, approximately 
 63 participants will receive 500 mg sotrovimab (62.5 mg/mL) into dorsogluteal muscles on Day 1. 63 participants will receive 500 mg sotrovimab (100 mg/mL) into dorsogluteal muscles on Day 1. 32 participants will receive 500 mg sotrovimab (100 mg/mL) into anterolateral thigh muscles on Day 1. 32 participants will receive 500 mg sotrovimab (100 mg/mL) into deltoid muscles on Day 1. In Part C Cohort 1: approximately 200 participants will receive IV Infusion of sotrovimab at 3000 mg dose infused over 60 minutes (100 mg/mL, diluted as per pharmacy manual). Part C enrollment will not be linked to Part A enrollment.
Study Intervention Assignment	
 This is an open-label study; however, the specific intervention to be administered to a participant will be assigned using an Interactive Voice/Web Response (IVRS/IWRS). In Part A, participants will be stratified by sex and two body mass index (BMI) strata (18 to \leq25 and $>$25 to 30 kg/m²) to aim for a balance of treatment arms within each stratum in the study. Sentinel cohorts in each study part are not required to be balanced by sex and BMI strata.
Time & Events	
 Refer to Section 6.3 Appendix 2 Schedule of Activities
Interim Analysis	
 An interim analysis (IA) for Part A will be performed once approximately half of the participants in Part A complete at least Day 8. An IA for Part C will be conducted after approximately half of the participants in Part C Cohort 1 complete at least Day 15. 
Please refer to Section 4.5 for more details.

2. STATISTICAL HYPOTHESES

Part A:

The primary objectives are to estimate the relative bioavailability, safety, and tolerability of single-dose high-concentration sotrovimab administered intramuscularly in healthy participants. There are no formal statistical hypotheses planned.

An estimation approach will be used to describe the pharmacokinetics of sotrovimab. An assessment of relative bioavailability with concentration effect (100 mg/mL IM sotrovimab into dorsogluteal muscles vs. 62.5 mg/mL IM sotrovimab into dorsogluteal muscles), and injection site effect (100 mg/mL IM sotrovimab into anterolateral thigh and deltoid vs. 62.5 mg/mL IM sotrovimab into dorsogluteal muscles) will be conducted for selected pharmacokinetic parameters, where point estimates along with 90% CI will be reported, where appropriate.

Part C:

The primary objectives are to characterize the safety and tolerability of IV sotrovimab administered in healthy participants. There are no formal statistical hypotheses planned.

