4.2. Primary Endpoint(s)/Estimands Analyses

4.2.1. Pharmacokinetics

4.2.1.1. Estimands

Table 1 Primary Estimand for Primary Pharmacokinetics Endpoint (Part A)

Primary Estimand	
Population	Male or female healthy participants aged 18 to 65 years who would be able to complete the IM dose
Variable/Endpoints	Sotrovimab serum PK parameters: AUC_{D1-29} and C_{max}
Treatment	100 mg/mL IM sotrovimab vs 62.5 mg/mL IM sotrovimab (dorsogluteal injections)
Strategy for Intercurrent Events or Events Leading to Missing Data	The intercurrent event of interest is participants receiving an incomplete IM dose. The strategy for handling this intercurrent event will be a Principal Stratum Strategy, where we are only interested in the strata of participants who would be able to receive a complete IM dose. Exclusion of participants who did not receive a complete IM dose will not introduce bias as the reasons for dose interruption are not related to their PK.
Population-Level Summary	The point estimate for the ratio of the geometric means of 100 mg/mL treatment group compared to the 62.5 mg/mL treatment group and the related 90% CI will be calculated.

Log-transformed parameters (AUC_{D1-29} and C_{max}) will be compared between treatment groups using ANCOVA models that include all four treatment groups, sex, and BMI (in kg/m^2) as variables. Least square estimates of treatment differences (contrasts for each comparison of interest) will be back-transformed to estimate relative bioavailability with two-sided 90% CIs. This analysis will be based on the PK Principal Stratum Analysis Set in Part A.

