4.3.1.3. Main Analytical Approach

The secondary pharmacokinetic analyses will be based on the PK analysis set in all study parts, unless otherwise specified. Available data will be analyzed as collected regardless of intercurrent events that may occur (treatment policy). Missing data will not be imputed.

Drug concentration measures

Concentrations of sotrovimab in serum through Day 29 and Week 24 will be listed for all participants by actual time and summarized by treatment arm, concentration and nominal time. Standard summary statistics will be calculated (i.e. n, arithmetic mean, 95% CI, standard deviation, median, minimum, maximum, %CV_b, 5th and 95th percentiles). Refer to the R&D Guideline: Non-Compartmental Analysis of Pharmacokinetic Data, GUI_000722 (v6.0), for more information regarding the treatment of serum concentrations that are BLOQ.

Individual serum concentration-time profiles and median/mean profiles by treatment arm and by concentration will be plotted for each participant within one figure both on the untransformed scale (i.e. a linear plot) and on the log transformed scale (i.e. log-linear plot). See [OPS](#) Section 2 List of Data Displays/ TFL Table of Content for details.

Derived Pharmacokinetic Parameters

Parameters will be summarized according to the method defined in Section [4.3.1.1](#) as described below. Individual participant PK parameter values and a descriptive summary will be reported by treatment arm (for all study parts) and by concentration (for Part A only). Data display specifications for derived PK parameter summaries and listings are provided in [OPS](#) Section 2 List of Data Display/ TFL Table of Content.

Table 6 Summary Statistics for Transformed and Untransformed PK Parameters

Untransformed Data: all parameters	n, arithmetic mean, 95% CI for the arithmetic mean, SD, median, minimum, maximum, %CV _b (percent coefficient of variation between subjects)
Log _e -transformed Data: all parameters except for T _{max} , T _{last} , t _{1/2} , and λ _z	n, geometric mean, 95% CI for the geometric mean, SD of log _e -transformed data and %CV _b

The following statistical analyses will also be performed for the following derived PK parameters from evaluable participants. Evaluable participants are defined as those who have sufficient PK concentration data to allow estimation of PK parameters used for secondary endpoint analysis (i.e., AUC_{D1-29} and C_{max}).

Part A:

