For Part A, the comparisons of relative bioavailability on Day 29 will be conducted for 100 mg/mL IM sotrovimab at 2 alternative injection sites (anterolateral thigh and deltoid) relative to the 62.5 mg/mL formulation administered dorsogluteally.

1. Injection Site Effect on Relative Bioavailability (for Part A Day 29 SAC)
Endpoint(s)
• C _{max} , AUC _{D1-29}
Model Specification

 log_e-transformed values of endpoints will be statistically analyzed separately using ANCOVA with the following terms: 
 Dependent variable: C_{max}, AUC_{D1-29} Covariates: sex, baseline BMI, treatment (62.5 mg/mL IM sotrovimab into dorsogluteal muscles, 100 mg/mL IM sotrovimab into dorsogluteal muscles,

1. Injection Site Effect on Relative Bioavailability (for Part A Day 29 SAC)

100 mg/mL IM sotrovimab into anterolateral thigh and 100 mg/mL IM sotrovimab into deltoid)

Data will be analyzed for PK Principal Stratum Analysis Set in Part A.

Point estimates and their associated 90% CI will be constructed for the differences in PK parameter values between the test injection sites (100 mg/mL IM sotrovimab [anterolateral thigh], 100 mg/mL IM sotrovimab [deltoid]) and reference injection site (62.5 mg/mL IM sotrovimab [dorsogluteal muscles]). The point estimates and their associated 90% CIs will then be back transformed to provide point estimates and their 90% CIs for the ratios, test/reference in PK parameter values on the original scale.

- The Kenward and Roger method for approximating the denominator degrees of freedom and correcting for bias in the estimated variance-covariance of the fixed effects will be used.

Model Checking & Diagnostics

- For ANCOVA, model assumptions will be checked, and appropriate adjustments may be applied based on the data.
- Distributional assumptions underlying the model used for analysis will be examined by obtaining a normal probability plot of the residuals and a plot of the residuals versus the fitted values (i.e., checking the normality assumption and constant variance assumption of the model respectively) to gain confidence that the model assumptions are reasonable

Model Results Presentation

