- Geometric least-squares means for each treatment (100 mg/mL IM sotrovimab into anterolateral thigh, 100 mg/mL IM sotrovimab into deltoid and 62.5 mg/mL IM sotrovimab into dorsogluteal muscles), point estimates and associated 90% CIs for the ratios (100 mg/mL IM sotrovimab [anterolateral thigh]:62.5 mg/mL IM sotrovimab [dorsogluteal muscles], 100 mg/mL IM sotrovimab [deltoid]:62.5 mg/mL IM sotrovimab [dorsogluteal muscles]) for each parameter will be produced in tabular format.
- Comparative plots of individual PK parameters will be generated on linear and semi-logarithmic scales.
- Plots of geometric mean ratio of test to reference treatment (100 mg/mL IM sotrovimab [anterolateral thigh]:62.5 mg/mL IM sotrovimab [dorsogluteal muscles], 100 mg/mL IM sotrovimab [deltoid]:62.5 mg/mL IM sotrovimab [dorsogluteal muscles]) together with 90% CIs will be produced.

In addition, for Part A, the comparisons of relative bioavailability at Week 24 will also be performed for 100 mg/mL IM sotrovimab at 3 injection sites (dorsogluteal, anterolateral thigh, and deltoid) relative to the 62.5 mg/mL formulation administered dorsogluteally.

2. Injection Site Effect on Relative Bioavailability (for Part A Week 24 SAC)

Endpoint(s)

- AUC_{inf}

Model Specification

2. Injection Site Effect on Relative Bioavailability (for Part A Week 24 SAC)

- \log_e -transformed values of endpoints will be statistically analyzed using ANCOVA with the following terms:
 - **Dependent variable:** AUC_{inf}
 - **Covariates:** sex, baseline BMI, treatment (62.5 mg/mL IM sotrovimab into dorsogluteal muscles, 100 mg/mL IM sotrovimab into dorsogluteal muscles, 100 mg/mL IM sotrovimab into anterolateral thigh and 100 mg/mL IM sotrovimab into deltoid)

Data will be analyzed for PK Principal Stratum Analysis Set in Part A.

- Point estimates and their associated 90% CI will be constructed for the differences in PK parameter values between the test treatment (100 mg/mL IM sotrovimab into dorsogluteal muscles, 100 mg/mL IM sotrovimab into anterolateral thigh, 100 mg/mL IM sotrovimab into deltoid) and reference treatment (62.5 mg/mL IM sotrovimab into dorsogluteal muscles). The point estimates and their associated 90% CIs will then be back transformed to provide point estimates and their 90% CIs for the ratios, test/reference in PK parameter values on the original scale.

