- The Kenward and Roger method for approximating the denominator degrees of freedom and correcting for bias in the estimated variance-covariance of the fixed effects will be used.

Model Checking & Diagnostics

- For ANCOVA, model assumptions will be checked, and appropriate adjustments may be applied based on the data.
- Distributional assumptions underlying the model used for analysis will be examined by obtaining a normal probability plot of the residuals and a plot of the residuals versus the fitted values (i.e., checking the normality assumption and constant variance assumption of the model respectively) to gain confidence that the model assumptions are reasonable

Model Results Presentation

- Geometric least-squares means for each treatment (100 mg/mL IM sotrovimab into anterolateral thigh, 100 mg/mL IM sotrovimab into deltoid, 100 mg/mL IM sotrovimab into dorsogluteal muscles and 62.5 mg/mL IM sotrovimab into dorsogluteal muscles), point estimates and associated 90% CIs for the ratios (100 mg/mL IM sotrovimab [anterolateral thigh]:62.5 mg/mL IM sotrovimab [dorsogluteal muscles], 100 mg/mL IM sotrovimab [deltoid]:62.5 mg/mL IM sotrovimab [dorsogluteal muscles], and 100 mg/mL IM sotrovimab [dorsogluteal muscles]:62.5 mg/mL IM sotrovimab [dorsogluteal muscles]) for each parameter will be produced in tabular format.
- Comparative plots of individual PK parameters will be generated on linear and semi-logarithmic scales.
- Plots of geometric mean ratio of test to reference treatment (100 mg/mL IM sotrovimab [anterolateral thigh]:62.5 mg/mL IM sotrovimab [dorsogluteal muscles], 100 mg/mL IM sotrovimab [deltoid]:62.5 mg/mL IM sotrovimab [dorsogluteal muscles], and 100 mg/mL IM sotrovimab [dorsogluteal muscles]:62.5 mg/mL IM sotrovimab [dorsogluteal muscles]) together with 90% CIs will be produced.

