4.8. Changes to Protocol Defined Analyses

There are no changes from the originally planned statistical analysis described in the protocol.

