5. SAMPLE SIZE DETERMINATION

The planned sample sizes for the number of evaluable participants in each treatment arm in Part A are based on precision estimation (using width of 90% CI) to assess the relative bioavailability. A sample size of approximately **50 evaluable participants** is selected for the two dorsogluteal arms in Part A (i.e., 500 mg IM of 62.5 mg/mL and 100 mg/mL sotrovimab arms, respectively) and approximately **25 evaluable participants** is selected for each of the 100 mg/mL sotrovimab anterolateral thigh and deltoid arms in Part A. Therefore, the total number of evaluable participants planned in this study is **150 in Part A**. To account for an expected 20% rate of non-evaluable participants approximately 190 participants will be randomized into Part A.

Sample size determinations are based on an assumed between participant CV_b for AUC_{D1-29}, AUC_{inf}, and C_{max} of 50%.

For the primary PK objective, assuming a point estimate of 1 for the ratio of each **primary PK endpoints** (i.e., AUC_{D1-29} and C_{max}) between the treatment arms under the variability assumptions and the planned sample size of evaluable participants described above, the 90% CIs are predicted to be:

Parameters	Treatment Comparison	Sample Size	CV _b	90% CI
AUC _{D1-29} and C _{max}	100 mg/mL sotrovimab dorsogluteal arm vs 62.5 mg/mL sotrovimab dorsogluteal arm	50 per arm	50%	(0.85, 1.17)

Similarly, for the secondary PK objective, assuming a point estimate of 1 for the ratio of each **secondary PK endpoints** (i.e., AUC_{D1-29}, AUC_{inf} and C_{max}) between the treatment arms under the variability assumptions and the planned sample size of evaluable participants described above, the 90% CIs are predicted to be:

Parameters	Treatment Comparisons	Sample Size	CV _b	90% CI
AUC _{D1-29} and C _{max}	100 mg/mL sotrovimab anterolateral thigh or deltoid arm vs 62.5 mg/mL sotrovimab dorsogluteal arm	25 vs 50	50%	(0.80, 1.25)
AUC _{inf}	100 mg/mL sotrovimab dorsogluteal arm vs 62.5 mg/mL sotrovimab dorsogluteal arm	50 per arm	50%	(0.85, 1.17)
AUC _{inf}	100 mg/mL sotrovimab anterolateral thigh or deltoid arm vs 62.5 mg/mL sotrovimab dorsogluteal arm	25 vs 50	50%	(0.80, 1.25)

Part C

The planned sample size for the number of evaluable participants in Part C Cohort 1 is 200. With 200 participants (intend to target up to approximately 20 Japanese

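### The SAP's site-effect contrasts change concentration as well as site, and no concentration-matched site ratio with an adjusted 90% CI is planned

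*SAP*

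**What the plan says.** SAP Section 2 separates two effects. The concentration effect is 100 vs 62.5 mg/mL, both dorsogluteal. The other is the "injection site effect (100 mg/mL IM sotrovimab into anterolateral thigh and deltoid vs. 62.5 mg/mL IM sotrovimab into dorsogluteal muscles").

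Section 4.3.1.3 then has two analysis blocks, titled "1. Injection Site Effect on Relative Bioavailability (for Part A Day 29 SAC") and "2. Injection Site Effect on Relative Bioavailability (for Part A Week 24 SAC"). Every ratio in them has 62.5 mg/mL dorsogluteal as denominator. The Week 24 block also contains "100 mg/mL IM sotrovimab [dorsogluteal muscles]:62.5 mg/mL IM sotrovimab [dorsogluteal muscles"], in which the site does not change.

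The model is common to all of these. Section 4.2.1.1 specifies "ANCOVA models that include all four treatment groups, sex, and BMI", and Section 4.3.1.3 repeats the same four treatment levels. The 100 mg/mL dorsogluteal arm is therefore fitted each time, but it never serves as the reference.

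SAP Section 5 and Protocol Section 9.5 both give an expected 90% CI of (0.80, 1.25) for the "100 mg/mL sotrovimab anterolateral thigh or deltoid arm vs 62.5 mg/mL sotrovimab dorsogluteal arm" at 25 vs 50 evaluable participants and a CV of 50%. SAP Section 4.8 states: "There are no changes from the originally planned statistical analysis described in the protocol".

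**The concern.** A ratio titled as a site effect will be read as what happens when the injection site changes. Here concentration changes too. If site made no difference at all, the titled ratio would simply equal the concentration ratio.

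Protocol Section 2.1 gives Part A two purposes: supporting the move to 100 mg/mL, and exploring thigh and deltoid as further sites. At the new concentration, the site comparison is thigh or deltoid against dorsogluteal, all at 100 mg/mL. That comparison is randomized and estimable from the planned models, but the SAP text does not ask for it. The Week 24 block adds to the confusion by filing a same-site ratio, which Section 2 calls a concentration effect, under the site title.

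The interval in Section 5 is a separate matter. It states the precision of these same contrasts and disagrees with its own inputs.

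**Working it through.** **The label.** On the log scale,

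log(thigh 100 / dorsogluteal 62.5) = log(thigh 100 / dorsogluteal 100) + log(dorsogluteal 100 / dorsogluteal 62.5).

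The documents give no value for the last term. As an illustration, take the plan's own predicted primary interval, (0.85, 1.17), as a range for the concentration ratio. The titled ratio is then 0.85 to 1.17 times the matched site ratio: 15% below to 17% above. At the plan's assumed ratio of 1 there is no difference.

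**Inputs for the intervals** (SAP Section 5, Protocol Section 9.5): CV 50%; true ratio 1; 50 evaluable in each dorsogluteal arm and 25 in each of thigh and deltoid, 150 in all; two-sided 90% CI.

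Formulas: σ = √ln(1 + 0.5²) = 0.4724; SE = σ√(1/n₁ + 1/n₂); limits = exp(± t₀.₉₅ × SE).

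| Comparison | SE | df | t | Half-width | 90% CI | Stated |
|---|---|---|---|---|---|---|
| 50 vs 50 | 0.0945 | 98 | 1.661 | 0.1569 | (0.855, 1.170) | (0.85, 1.17) |
| 25 vs 50 | 0.1157 | 73 | 1.666 | 0.1928 | (0.825, 1.213) | (0.80, 1.25) |
| 25 vs 50, ANCOVA df | 0.1157 | 150 − 6 = 144 | 1.656 | 0.1916 | (0.826, 1.211) | (0.80, 1.25) |
| 25 vs 25 | 0.1336 | 48 | 1.677 | 0.2241 | (0.799, 1.251) | not stated |

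The method reproduces the primary interval but not the 25 vs 50 one. The stated half-width is ln(1.25) = 0.2231, and 0.2231/0.1916 = 1.16, so it is 16% too wide on the log scale. It matches 25 vs 25. At 25 vs 50 it would need a CV of about 59% (58% to 61% allowing for rounding of the upper limit).

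**Precision of the missing contrast.** Thigh or deltoid vs 100 mg/mL dorsogluteal is also 25 vs 50, so its SE is again 0.1157 and its expected 90% CI is (0.83, 1.21) with 144 df. Simulating the four-arm ANCOVA with sex and BMI (4,000 runs, arms of 50/50/25/25) gave a mean half-width of 0.192 for thigh vs 62.5 mg/mL dorsogluteal and for both matched contrasts.

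**What a reader could recover without it.**

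- *Point ratio:* available from the planned least-squares means.
- *Dividing the two planned ratios as if independent:* SE = √(0.1157² + 0.0945²) = 0.1494, giving (0.78, 1.28). This is too wide, because the two ratios share the 62.5 mg/mL arm.
- *Unadjusted CI:* SAP Table 6 gives "n, geometric mean, 95% CI for the geometric mean" by arm, from which an interval can be built. Its half-width is 0.1928. The adjusted half-width is 0.1916, 0.1817, 0.1713 or 0.1603 if sex and BMI explain 0, 10, 20 or 30% of the log variance (an assumed range). The unadjusted interval is then 1.01, 1.06, 1.13 or 1.20 times as wide.
- *Borrowing the half-width of the planned thigh or deltoid contrast:* a fair approximation when the two dorsogluteal arms end up the same size.

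**The case against.** The planned contrasts answer the stated objectives. Every Part A bioavailability objective uses 62.5 mg/mL dorsogluteal as reference, and none asks for a site ratio within 100 mg/mL. This stands, and is why the contrasts should be kept.

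The ratios are spelled out arm by arm, and the concentration ratio is reported with its own 90% CI, so a careful reader can see that two things change. This stands too, and limits the harm from the title.

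Little is lost numerically. In simulation with 50/50/25/25, the SE of the matched contrast was within about 1.5% of the planned contrast's SE in 95% of runs. If attrition left 40 and 55 in the dorsogluteal arms, the gap would be about 6%: √(1/25 + 1/40) / √(1/25 + 1/55) = 1.06. So the borrowed interval is close. It remains an approximation that each reader would have to construct, in place of one the model gives directly.

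The 15% to 17% range is not an estimate of bias. It treats a predicted sampling interval as a range for an unknown ratio, and is offered only on that condition.

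Matching on concentration does not isolate site completely. Protocol Table 4 gives the 62.5 mg/mL arm two 4 mL injections; Section 9.3.1 describes 100 mg/mL dorsogluteal as one 5 mL injection; and the deltoid limit of 2.5 mL per injection means at least two injections for the 5 mL dose. The safety review team may also change the number of injections by arm. This stands and calls for a footnote.

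Finally, the Output and Programming Specification was not available and may list further displays. The point is confined to the SAP text, where the model contrasts are specified.

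**Conclusion.** The concern holds, as a change that should be made rather than a threat to the trial. The site-effect title is wrong on the SAP's own distinction between concentration and site. The one adjusted comparison that holds concentration fixed is not specified, although every planned model already contains the data for it. What is missing is the exact adjusted CI, and Protocol Section 4.2 names BMI and sex as main determinants of exposure. Only secondary, descriptive PK is affected: no hypothesis, primary result or error rate changes.

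The size of the labelling problem depends on the unknown concentration ratio. It is nil at 1 and reaches −15% or +17% at the ends of the plan's predicted interval.

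The (0.80, 1.25) interval is wrong for its stated inputs in both documents. The error is conservative and leaves the sample size adequate.

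**What to change.** 1. In SAP Section 4.3.1.3, add thigh vs dorsogluteal and deltoid vs dorsogluteal, all at 100 mg/mL, with 90% CIs from the same ANCOVA models for AUC(D1-29), Cmax and AUC(inf). Title them *concentration-matched site comparison* and record the addition in SAP Section 4.8.
2. Keep the thigh and deltoid contrasts against 62.5 mg/mL dorsogluteal, retitled *combined concentration-and-site comparison* in Sections 2 and 4.3.1.3. Report the Week 24 dorsogluteal ratio as a concentration effect.
3. Footnote all these contrasts, including 100 vs 62.5 mg/mL dorsogluteal, to say that the number and volume of injections may also differ between arms.
4. Separately, correct the expected 25 vs 50 interval in SAP Section 5 and Protocol Section 9.5. It should be about (0.82, 1.21) by the two-sample method that reproduces (0.85, 1.17), or (0.83, 1.21) with the ANCOVA degrees of freedom. Alternatively, state the inputs that give (0.80, 1.25). Until the protocol is amended, note the discrepancy in SAP Section 4.8; a note beside the Section 5 table would serve as well if 4.8 is reserved for changes to analyses.

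The cost is two extra estimate statements per model, new titles, a footnote, an entry in 4.8 and one corrected interval in each document. No new data or participants are needed. The downside is two more descriptive ratios per parameter, in a study with no formal hypotheses and no multiplicity adjustment.
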